Title: Effect to Gastrointestinal Barrier Function During Laparoscopic Gastrectomy with Deep vs Moderate Neuromuscular Blockade

NCT number: NCT03782233

Date: 2018-11-05

Study Protocol and Statistical Analysis Plan

Study Protocol

1. Perioperative vital signs and surgical conditions

Arterial blood pressure, heart rate, pulse oxygen saturation and other perioperative vital signs in moderate neuromuscular blockade group (group M) and deep neuromuscular blockade group (group D) will be recorded. Volume of perioperative blood loss and infusion volume (including crystalloid solution, colloidal solution and blood products) will be recorded either. Surgical condition scores, intraoperative pressure of CO₂ pneumoperitoneum and duration of pneumoperitoneum will be recorded. Blood gas analysis will be performed hourly during the operation.

2. Extubation

After the operation, the extubation time of patients in the two groups and the modified Aldrete score at 1min, 5min and 15min after the extubation will be recorded.

3. Postoperative pain scores

Assessment and record of Visual analogue scale (VAS) at rest and activity 6 h, 12 h, 24 h, 48 h after extubation. (VAS pain score: 0 - completely painless, 10 - unbearable pain.)

4. Evaluations of intestinal barrier function

4.1 The concentrations of d-lactic acid and diamine oxidase

5ml peripheral venous blood will be extracted from the patients of the two groups on the first day before surgery and the first day after surgery for plasma d-lactic acid level and diamine oxidase activity detection.

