SPSS 20.0 software will be used for statistical analysis. The measurement data will be tested by t test or Mann-Whitney U test. The data will be expressed as mean \pm standard deviation. Nominal variables are summarized as number of subjects (proportion, %) and will be compared with the Chi-square test or Fisher's exact probability. $P < 0.05$ will be considered statistically significant. On the basis of the primary parameters, we estimated that 83 patients will be needed with an α error of 0.05, a β error of 0.2 and a drop-out rate of about 10%.

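### Free improvement: d-lactic acid and diamine oxidase are measured before and after surgery, but the planned t or Mann-Whitney test makes no use of the baseline and the tested quantity is unstated

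*Combined protocol and SAP*

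**What the plan says.** Section 4.1 has blood drawn from both groups "on the first day before surgery and the first day after surgery for plasma d-lactic acid level and diamine oxidase activity detection". Both markers therefore have one preoperative and one postoperative value per patient.

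The Statistical Analysis Plan has one sentence on testing continuous variables: "The measurement data will be tested by t test or Mann-Whitney U test". They are to be summarised by mean and standard deviation. No covariate, regression model, change score or repeated-measures analysis is named anywhere in the document, and nothing says which quantity is compared between groups.

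On size, the same paragraph says: "On the basis of the primary parameters, we estimated that 83 patients will be needed", with α 0.05, β 0.2 and about 10% drop-out. The primary parameters are not named.

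**The concern.** There are two gaps, and one change closes both.

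- **The tested quantity is open.** The comparison could be of postoperative values or of changes, each by t test or Mann-Whitney. That is four possible analyses per marker, and nothing prevents the choice being made after the data are seen. This gap does not depend on any assumed correlation.
- **The baseline is collected but not used well.** Testing postoperative values amounts to fixing the slope on baseline at 0. Testing change fixes it at 1. ANCOVA estimates the slope from the data, and it also corrects a chance difference between groups at baseline.

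At stake are the precision of the comparison and the bias in a particular trial whose groups happen to differ at baseline. Type I error is not at stake if allocation is random. These markers come under the heading on evaluation of intestinal barrier function, which is the subject of the trial's title, so they matter even if they are not primary.

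**Working it through.** **Inputs.** From the Statistical Analysis Plan: 83 patients, α 0.05, β 0.2, drop-out about 10%. Assumed, because the document does not give them: 83 is the total, 1:1 allocation, two-sided test, normal data, a common baseline slope, and pre-post correlation r and SD ratio k = SD_post/SD_pre over a range.

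**The plan's own figure.** It cannot be reproduced forward, because no effect size or SD is stated. Working back, 83 × 0.9 = 74.7, so 37 evaluable per group. The standardised difference d (in postoperative SD units) that gives an unadjusted t test 80% power at n = 37 per group is 0.66. As a check, the normal-approximation formula gives 2 × (1.960 + 0.842)² / 0.66² = 36.05, rounded up to 37 per group, and 74 / 0.9 = 82.2, rounded up to 83. This is a back-solution, and the document does not say that the trial was sized on these markers.

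**Power formula.** Noncentral t, with noncentrality d × √(n/2) / √V. V is the variance relative to that of the postoperative value:

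- postoperative value: V = 1, df = 2n − 2
- ANCOVA: V = 1 − r², df = 2n − 3
- change: V = 1 + 1/k² − 2r/k, df = 2n − 2

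For example, the unadjusted noncentrality is 0.66 × √18.5 = 2.84 (power 80%). With ANCOVA at r = 0.5 it is 2.84 / √0.75 = 3.28 (power 90%).

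| Analysis | r = 0.2 | r = 0.3 | r = 0.5 | r = 0.7 |
|---|---|---|---|---|
| t test, postoperative value | 80% | 80% | 80% | 80% |
| ANCOVA | 82% | 84% | 90% | 98% |
| t test on change, k = 1 | 60% | 66% | 80% | 95% |
| t test on change, k = 2 | 78% | 82% | 90% | 97% |
| t test on change, k = 0.5 | 28% | 30% | 37% | 47% |

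ANCOVA standard errors are smaller than unadjusted ones by 1 − √(1 − r²), which is 5%, 13% and 29% at r = 0.3, 0.5 and 0.7.

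**When change is worse than ignoring the baseline.** V for change exceeds 1 when r < 1/(2k) = SD_pre/(2 × SD_post). This is the familiar 0.5 only if the two SDs are equal.

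**Simulation** (20,000 trials per setting, normal data). ANCOVA power was about 83%, 89% and 97% at r = 0.3, 0.5 and 0.7, and Mann-Whitney on postoperative values about 78%. The cost of estimating the slope shows at r = 0, where ANCOVA had about 79.4% against 80.0% for the t test. At r = 0.5 and k = 2, where a slope of 1 is exactly right, ANCOVA had 89.4% against 89.7% for change. Type I error at r = 0.5 was 0.051 for both the unadjusted t test and ANCOVA (40,000 trials).

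**Chance imbalance.** The baseline difference has standard error √(2/37) = 0.23 SD, so it exceeds 0.3 SD in either direction in 20% of trials. At r = 0.5, a 0.3 SD difference moves the unadjusted estimate by 0.5 × 0.3 = 0.15 SD.

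**If 83 is per group.** With 75 evaluable per group, d = 0.46 gives 80% unadjusted power and the ANCOVA figures are unchanged. The baseline standard error becomes √(2/75) = 0.16 SD, and the 20% becomes 7%.

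**The case against.** The case on the other side has five parts.

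1. **The plan says only t test, not two-sample t test.** True. Two-sample is the natural reading beside Mann-Whitney U in a two-group trial, but a paired test within each group is not excluded. That would add to the ambiguity rather than remove it.
2. **This is a preference about efficiency, not an error.** It is right that the planned test stays valid under random allocation, and nothing here says otherwise. It does not answer the unstated tested quantity.
3. **The gain may be negligible.** This stands as a limit. Major surgery falls between the two samples, so a low correlation is possible. At r = 0.1, ANCOVA power is 80.4% by formula, before the half-point cost seen in simulation. The worst case is therefore a loss of about half a point. The power figures also borrow the trial's 80% for markers that may not be primary.
4. **ANCOVA on the wrong scale is worse than the plan.** This is the strongest point. In simulated lognormal data (log-scale d = 0.66, log SD 1, 37 per group), raw-scale ANCOVA had 62%, 64% and 68% power at r = 0.1, 0.3 and 0.5, against 77–78% for Mann-Whitney on postoperative values. Log-scale ANCOVA had 80%, 83% and 89%. The advantage therefore depends on choosing the scale properly, which is why the fix sets it in advance and keeps the planned test alongside. Preoperative values alone may also fail to show skewness that appears only after surgery.
5. **The precision claim needs a common slope or equal allocation.** Correct, and the allocation ratio is not stated. The figures assume both.

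None of this restores a reason to leave the baseline unused or the tested quantity undefined.

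**Conclusion.** The concern holds. The plan collects a baseline for both plasma markers, plans no adjustment for it, and does not define what is compared. Under the stated assumptions, ANCOVA adds about 4, 10 and 18 power points over an unadjusted t test at r = 0.3, 0.5 and 0.7, and under two points at r = 0.2 or less. The undefined choice matters as well: at r = 0.3 with equal SDs, testing change rather than the postoperative value drops power from 80% to 66%.

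These sizes are illustrative, because effect size, SDs, correlation and allocation ratio are all assumed. The conclusion that ANCOVA is at least as precise as either alternative, apart from the small cost of estimating the slope, rests on a suitable scale and a common slope or equal groups. Whether the trial's main result is affected cannot be determined, since the primary parameters are not named. The change should be made, but the trial's validity does not depend on it.

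**What to change.** Add to the Statistical Analysis Plan:

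- Postoperative day-1 d-lactic acid and diamine oxidase will each be compared between groups by ANCOVA, with the preoperative value of the same marker as covariate.
- The scale (raw or log) will be fixed before the group comparison is seen, for example from the preoperative values pooled over both groups. On the log scale, outcome and covariate are both logged. Pooled postoperative values without group labels could be inspected too, to catch skewness that arises only after surgery.
- The adjusted difference, or ratio if logged, will be reported with its 95% confidence interval.
- The t or Mann-Whitney test on postoperative values will be kept as a sensitivity analysis.

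The cost is a few sentences. No new patients, samples or data are needed, and the analysis runs in the software already named.

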4.2 Parameters of intestinal mucosal

(1) After the removal of gastric tumor, jejunum tissues of the two groups of patients will be collected. The height, width and number of villi in the intestinal mucosa will be observed and determined by microscopy. The density of mitochondria, length and width of villi, and clearance of intestinal epithelial cells will be analyzed by scanning electron microscopy to detect the damage of intestinal mucosal mechanical barrier.

(2) The expression level of sIgA⁺ in the submucosal lamina propria will be detected by immunohistochemistry to reflect the damage of intestinal mucosal immune barrier.

5. Intestinal microecology

The change of intestinal mucosal biological barrier function was reflected mainly through selective bacterial culture of feces. The first, second, third and one-month postoperative defecation of the patients in two groups before and after surgery will be

collected and analyzed with the following methods:

- (1) Routine examination of feces;
- (2) Selective culture of aerobic bacteria (such as Enterococcus, Enterobacter spp.) and anaerobic bacteria (such as Bifidobacteria, Lactobacillus), calculate the ratio of Bifidobacteria to Escherichia Coli. (B/E value), which is an important indicator to evaluate the status of intestinal flora, in the health condition, B/E value should be at least >10 , otherwise it is regarded as flora imbalance;
- (3) 16S rRNA sequencing of the feces to analyzed the microbiota;
- (3) Determine the pH of feces;
- (4) Determination of fecal ammonia.

6. The postoperative recovery of intestinal function

The postoperative recovery of intestinal function in the two groups will be evaluated, including the first postoperative exhaust time, defecation time and feeding time, time of removal of abdominal drainage tube, postoperative hospital stays the incidence of diarrhea and abdominal distension within one month after operation.

Statistical Analysis Plan

SPSS 20.0 software will be used for statistical analysis. The measurement data will be tested by t test or Mann-Whitney U test. The data will be expressed as mean \pm standard deviation. Nominal variables are summarized as number of subjects (proportion, %) and will be compared with the Chi-square test or Fisher's exact probability. $P < 0.05$ will be considered statistically significant. On the basis of the primary parameters, we estimated that 83 patients will be needed with an α error of 0.05, a β error of 0.2 and a drop-out rate of about 10%.

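### The stool schedule implies a preoperative sample but never specifies one, and the SAP names no method that uses a baseline value

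*Combined protocol and SAP*

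**What the plan says.** Protocol section 5 states its purpose as follows: "The change of intestinal mucosal biological barrier function was reflected mainly through selective bacterial culture of feces". The schedule is "The first, second, third and one-month postoperative defecation of the patients in two groups before and after surgery will be" collected and analysed. The assays are routine examination, selective culture with the Bifidobacteria to E. coli ratio (B/E), 16S rRNA sequencing, pH and ammonia. For B/E the protocol expects a value above 10 in health; "otherwise it is regarded as flora imbalance".

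Section 4.1 is explicit for the blood markers. Samples are taken "on the first day before surgery and the first day after surgery for plasma d-lactic acid level" and diamine oxidase activity.

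Section 6 lists recovery outcomes, among them "the first postoperative exhaust time, defecation time and feeding time".

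The SAP gives one rule per data type for all outcomes. For continuous data: "The measurement data will be tested by t test or Mann-Whitney U test". Nominal variables "will be compared with the Chi-square test or Fisher's exact probability". It mentions no baseline value, change score, covariate or repeated-measures method. On size it says: "On the basis of the primary parameters, we estimated that 83 patients will be needed", without naming those parameters.

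**The concern.** The stool sentence contradicts itself. Its list is postoperative throughout, while its closing words and the section's aim call for a comparison with the preoperative state. Two people following it could collect different sets of samples. If the list is taken literally, no within-patient change can be computed, and a preoperative stool that was missed cannot be recovered after the operation.

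If a preoperative stool is taken, the SAP does not say what it is for. A t or Mann-Whitney test could be run on postoperative values or on changes, and the two differ in precision by an amount that depends on the correlation between baseline and follow-up. Neither is as precise as a baseline-adjusted comparison, except at extreme correlations where the difference vanishes.

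The same gap is certain, not conditional, for d-lactic acid and diamine oxidase: their preoperative values are scheduled, and the SAP gives them no role.

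**Working it through.** **1. The texts side by side.** Named stool samples: first, second, third and one-month, so 0 of 4 are preoperative on the natural reading. Blood markers: one named day before surgery and one after. The protocol therefore fixes a baseline day for blood and none for stool. On a looser reading, in which the qualifier for the postoperative period attaches only to the one-month sample, some of the first three stools could fall before surgery. Their number and timing would still be undefined.

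**2. The plan's own figure.** The 83 cannot be reproduced, because no effect size, SD or event rate is given. Only the drop-out step can be followed: 74/0.9 = 82.2, rounded up to 83 (or 75 × 1.1 = 82.5, rounded up to 83). Whether 83 is the total or per group is not stated.

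**3. Inputs for the precision check.** From the SAP: alpha 0.05, power 80%, drop-out about 10%. Assumed: a two-sided test, equal groups, normal data, equal SD before and after surgery, and a correlation ρ between baseline and follow-up of 0.1, 0.3, 0.5 or 0.7. If 83 is the total, 83 × 0.9 = 74.7, or about 37 evaluable per group. If it is per group, about 74 each.

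**4. Formulas.** The detectable difference d on postoperative values comes from the noncentral t distribution: 0.660 SD at 37 per group and 0.464 SD at 74. For change scores, multiply d by √(2(1 − ρ)). For ANCOVA, multiply by √(1 − ρ²), with one degree of freedom lost. At 37 per group and ρ = 0.5, for example, the change score gives 0.660 × 1 = 0.660 and ANCOVA gives 0.660 × 0.866 = 0.572.

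**5. Results at 37 per group** (detectable difference in SD of the stool measure)

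| ρ | Postoperative value | Change score | ANCOVA | ANCOVA below the better simple test |
|---|---|---|---|---|
| 0.1 | 0.660 | 0.886 | 0.657 | 0.5% |
| 0.3 | 0.660 | 0.781 | 0.630 | 4.6% |
| 0.5 | 0.660 | 0.660 | 0.572 | 13.4% |
| 0.7 | 0.660 | 0.511 | 0.472 | 7.8% |

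At 74 per group: postoperative 0.46; change score 0.62 / 0.55 / 0.46 / 0.36; ANCOVA 0.46 / 0.44 / 0.40 / 0.33.

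**6. Power for a 0.5 SD difference, 37 per group.** Postoperative values 56%; change scores 35 / 43 / 56 / 78%; ANCOVA 57 / 60 / 69 / 84%. The unstated choice between the two simple tests moves power by about 21 points down at ρ = 0.1 (56 − 35) or 22 up at ρ = 0.7 (78 − 56). ANCOVA is at least as good as either throughout this range.

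**The case against.** The strongest reply is that this is a wording slip and the rest is preference. The reference to the time before surgery, together with the aim of measuring change, suggests that a baseline stool was always meant. A two-group test on postoperative values or changes is a legitimate method. The gain from ANCOVA rests on a correlation that the documents do not give, and at 0.1 it is negligible. The calculation also assumes normal data, whereas B/E is a ratio with a cut-off, sequencing output is not one continuous variable, and the SAP allows a rank test.

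Much of this stands. A reader might infer that the trial has no stool baseline. The documents do not support that; they leave its timing and number unstated. Nor do the figures show that the trial is underpowered, since the primary parameters are unnamed and nothing places stool measures among them.

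Two further inferences go too far. One is that lack of preoperative B/E prevents a comparison of imbalance. The protocol defines imbalance as a status at one sample, so proportions can be compared without classing cases as new or pre-existing. The other is that numbering stools by defecation, while defecation time is itself an outcome, undermines the comparison. That is a minor ambiguity, and section 6 already records defecation time.

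What the reply does not remove is that the sentence cannot be carried out uniformly as written, and that the SAP assigns no use to any baseline, including the blood values that are certainly scheduled.

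**Conclusion.** The point holds as an inconsistency to be reconciled and an analysis to be improved, and it should be acted on before stools are collected. Following the named list leaves the question about change unanswerable. Following the apparent intention produces a baseline that the SAP does not use.

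The gain in precision is modest and depends on assumptions: 0.5% to 13% in detectable difference against the better simple test, over correlations of 0.1 to 0.7, with normal data and equal SDs. Larger gaps, such as 28.6% at ρ = 0.7 against postoperative values, arise only against the weaker simple test at that correlation. No figure is offered for B/E.

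On validity, neither flat conclusion is supported. An unadjusted postoperative comparison is valid if the groups are comparable at entry, as randomisation would provide. The documents do not describe allocation, so they establish neither comparability nor its absence.

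**What to change.** - Rewrite the section 5 sentence so that one preoperative stool, with its collection time and the same assays, is listed explicitly beside the four postoperative samples.
- In the SAP, compare continuous stool measures by ANCOVA on the preoperative value, or by a mixed model over the four postoperative samples with that value as a covariate. Use a transformed or rank-based version if the data are skewed. With the baseline as covariate, the adjusted group difference is the same whether the outcome is the postoperative value or the change, so this answers the stated question.
- Apply the same adjustment to d-lactic acid and diamine oxidase, using the preoperative values already scheduled in section 4.1.
- Optional and descriptive: report B/E imbalance by preoperative status, and record the date of each stool. Dates help interpretation but do not remove the ambiguity of sampling by defecation number.

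The cost is clearer wording and slightly more analysis. Only if a preoperative stool was not already intended, there is one extra non-invasive sample per patient with its assays. That is 83 on top of 83 × 4 = 332 if 83 is the total, or 166 on top of 166 × 4 = 664 if it is per group; 25% more either way. The blood markers need no new samples.
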